#### Training Trial to Test Learning Target Engagement.

**Training Trial Overview.** Therapists seeking exposure training (N=40) will be recruited to complete a training workshop in exchange for continuing education credits (CEs) and monetary compensation. Therapists will be randomly assigned to interact with one of the **SET™** delivery methods (i.e., HMD or WB). All therapists will receive the same 4-hour didactic instruction in exposure therapy followed by experiential VR training (2 hours) with the assigned delivery method. Our learning target (negative beliefs) measure will be given at multiple timepoints to isolate the specific, incremental effect of the experiential component on our beliefs target (see Table 1). The two conditions will operate as a tandem case-series analysis that evaluates whether therapists in both conditions reach an a-priori target engagement benchmark.

**Training Trial Outcome Measures.** **Therapist Negative Beliefs about Exposure Scale (TBES)**. The TBES assesses the extent to which therapists endorse 21 negative beliefs about exposure therapy. The TBES is the primary outcome measure for assessing target engagement. **Exposure Knowledge**. We have condensed the original 49 multi-choice item measure by selecting 12 multiple-choice items that best fit the didactic content of our training. **Exposure Self-Efficacy**. This is a 27-item measure of therapists' confidence in delivering exposure therapy. This measure has demonstrated high internal consistency and predictive validity in determining the frequency of self-reported clinical use of exposure therapy.

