## Analytic Plan

Statistical analyses were carried out using SAS version 9.4 1M7 (The SAS Institute, Cary NC). Knowledge, Self Efficacy, and TBES were assessed longitudinally and analyzed via binomial Generalized Estimating Equations (GEE). SUS, VPE, and TARS were only assessed at the conclusion of the study and were analyzed using a binomial generalized linear model. Both sets of analyses used the binomial distribution to constrain the model space to the range of the measures being used. The scores were first shifted to have a minimum score of zero by subtracting the minimum score possible. This was used as the binomial number of “successes”, and the range of the score was used as the number of “trials”. Classical sandwich estimation was then used to better incorporate any differences in empirical variances and covariances. Both raw and adjusted (where appropriate) p-values were presented as well as unadjusted 95% confidence intervals. For GEEs, 16 different hypotheses were tested using orthogonal linear estimates: a) changes from baseline conditions in each condition (8 total), b) high- and low-immersion training conditions compared at each time point cross sectionally (4), and as c) condition comparisons in changes from baseline for each follow-up (4). The Holm test was used to calculate adjusted p-values maintaining familywise alpha at 0.05 across all 16 hypothesis tests in GEEs. For all other models, only one hypothesis was tested comparing the conditions.

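### For each GEE outcome, HMD and WB appear to be compared twice at every follow-up, the two answers differ by the chance baseline difference, neither is named as decisive, and baseline is not used as a covariate

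*Combined protocol and SAP*

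**What the plan says.** The Analytic Plan fits a binomial GEE to each of TBES, Knowledge and Self Efficacy and states that "16 different hypotheses were tested using orthogonal linear estimates". They fall into three sets:

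- (a) "changes from baseline conditions in each condition (8 total")
- (b) "high- and low-immersion training conditions compared at each time point cross sectionally (4")
- (c) "condition comparisons in changes from baseline for each follow-up (4")

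All 16 enter one Holm family at 0.05 with equal standing. On reporting, the section says: "Both raw and adjusted (where appropriate) p-values were presented as well as unadjusted 95% confidence intervals". It names no covariate, no primary time point and no deciding between-arm contrast. It is written in the past tense ("Statistical analyses were carried out using SAS version 9.4 1M7").

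The Training Trial Overview makes allocation random ("Therapists will be randomly assigned to interact with one of the" two delivery methods) and frames the main aim within arms: "The two conditions will operate as a tandem case-series analysis that evaluates whether therapists in both conditions reach an a-priori target engagement benchmark". Research Objectives adds the goal of finding which platform best balances usability, target engagement and scalability, and glosses target engagement as change in negative beliefs. Subject Recruitment gives N=40.

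**The concern.** Under randomisation, (b) and (c) target essentially the same platform effect. Set (c) subtracts the baseline arm difference and (b) ignores it. That difference is noise, and with 40 therapists it can be large enough for the two estimates to tell different stories at the same follow-up. Eight of the 16 tests are therefore spent on what most naturally are four arm comparisons, and the reader has no rule for choosing between the two results. Neither set uses the collected baseline score in the way that usually gives the most precision, as a covariate.

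At stake is how clearly and precisely the platform comparison is reported. The within-arm benchmark question does not depend on it.

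**Working it through.** **Count.** Set (a): 2 arms × 4 follow-ups = 8. Set (c): 4 follow-ups = 4. Set (b): 4. Total 8 + 4 + 4 = 16, which reproduces the plan's figure. Sets (a) and (c) imply baseline plus four follow-ups, so the four tests in (b) fit the same four follow-ups. If (b) counted baseline as one of its four time points, three follow-ups would be compared twice and one test would fall on a pure chance difference.

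**Structure.** Write the 16 contrasts on 2 arms × 5 occasions = 10 cell means. All four differences (b) − (c) are the same row, HMD minus WB at baseline. Sets (b) and (c) together are 8 tests of rank 5. All 16 have rank 9, and 62 of the 120 pairs have a non-zero inner product, so the set cannot be orthogonal.

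The identity holds on the link scale. Example with an assumed logit link and mean scores as proportions of range: baseline 0.50 vs 0.45, follow-up 0.30 vs 0.30. Then (b) = 0.00 and (c) = −0.20.

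**Size of the gap, no correlation needed.** Assume 20 per arm, because the allocation ratio is not stated. SE = √(1/20 + 1/20) = 0.316 SD. By the normal approximation the two estimates are more than 0.3 SD apart in 34% of trials and more than 0.5 SD apart in 11%. At 15:25 the figures are 36% and 13%.

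**Precision and disagreement.** The documents give no baseline-to-follow-up correlation, so r is varied. Relative variances are 1 for (b), 2(1 − r) for (c), and (1 − r²) × 37/36 for a baseline-adjusted contrast. The correlation between (b) and (c) is √((1 − r)/2). Disagreement means that exactly one of (b) and (c) is significant, two-sided, at a single follow-up under an assumed 0.5 SD effect. Detectable difference is (z for α/2 + 0.842) × SE, with α = 0.05/16 = 0.0031 for the better planned contrast and 0.05/12 = 0.0042 for the adjusted one.

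| r | Var (c) | Var adjusted | Reduction vs better of (b), (c) | Disagree, raw 0.05 | Disagree, 0.05/16 | Detectable at 80% power, planned → adjusted (SD) |
|---|---|---|---|---|---|---|
| 0.3 | 1.40 | 0.94 | 6% | 27% | 9% | 1.20 → 1.13 |
| 0.5 | 1.00 | 0.77 | 23% | 31% | 12% | 1.20 → 1.03 |
| 0.7 | 0.60 | 0.52 | 13% | 39% | 19% | 0.93 → 0.85 |
| 0.8 | 0.40 | 0.37 | 8% | 48% | 32% | 0.76 → 0.71 |

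The reductions at r = 0.4 and 0.6 are 14% and 18%. Break-even is r = 0.164, and at r = 0.1 the adjustment loses about 2%. With no true effect, disagreement is 8 to 9% at raw 0.05 and about 0.6% at 0.05/16.

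**Check in the planned model class.** Binomial GEE simulations (2,500 trials per scenario, 20 per arm, classical sandwich, no missing data, assumed ranges of 84 for TBES and 12 for Knowledge) gave gains of 6 to 22% at observed r of 0.25 to 0.79 for TBES and for Knowledge without added noise. For a noisy 12-item score the gains were 0.4, 2, 11 and 15% at observed r of 0.14, 0.24, 0.33 and 0.38. Raw type I error at nominal 0.05 was 0.055 to 0.072 for (b) and (c), and 0.060 to 0.075 adjusted.

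**The case against.** The case on the other side is substantial.

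- **Nothing is invalid.** A reader might infer that testing the arms twice inflates the error rate. The documents do not support that: Holm covers all 16 tests and is valid under dependence. Only the raw p-values and unadjusted intervals lack that protection, and the plan labels the intervals as unadjusted.
- **The 27 to 48% figures are not the plan's error-controlled conflict rate.** They apply at raw 0.05. They are relevant only because raw p-values are also presented. At the first Holm threshold the range is 9 to 32%.
- **The comparison is secondary.** The stated design is a within-arm benchmark, and the gloss of target engagement as belief change already leans towards (c) for TBES. It does not do so for Knowledge or Self Efficacy, and the Analytic Plan gives (b) equal standing throughout.
- **The results may be known.** The past tense suggests so. No test can then be dropped, the Holm and detectable-difference gains disappear, and an added adjusted contrast is a third estimate. A stated reading rule is needed to avoid adding to the confusion.
- **Adjustment breaks a tidy relation.** In the planned model (c) is exactly the difference between the two arms' (a) contrasts. A baseline-conditional arm effect from a second model is not.
- **The schedule is inferred from counts.** Table 1 is not in the text available. If it shows a score after the didactic session and before VR, that score might be the more relevant covariate.

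All of these stand as limits on the size of the point. None supplies the missing deciding contrast.

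**Conclusion.** The point holds as a modest one of precision and interpretation on the secondary platform comparison. Two results do not depend on r: the (b) and (c) estimates differ by the chance baseline difference (SE about 0.32 SD at an assumed 20 per arm), and the plan names neither as decisive. The efficiency gain from a baseline covariate does depend on r: about 6 to 23% of variance for r from 0.3 to 0.8, near nil for a noisy Knowledge score, and a small loss below about 0.16.

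A reader might also infer that adjustment would rescue the arm comparison. It would not: even under the best fix, the detectable difference at the first Holm step stays between 0.71 and 1.13 SD at the tabulated r.

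The conclusion assumes four follow-ups in set (b), equal allocation, two-sided tests, no dropout and a normal approximation. The disagreement rates also assume a 0.5 SD effect. That the adjustment is absent is read from the plan's silence on covariates.

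**What to change.** **If results are not yet known.** Replace (b) and (c) with one baseline-adjusted arm contrast per follow-up, from a binomial GEE on follow-up scores with arm, time, arm-by-time and baseline score. Keep the existing GEE for set (a), and apply Holm over 8 + 4 = 12 tests per outcome. Cost: SAP wording, a second model for each GEE outcome, a Holm family spanning two models, and an arm effect that is conditional on baseline and no longer equals the difference of the within-arm changes. No new data are needed.

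**If results are known.** Keep the 16 tests and their Holm family. Report the adjusted contrast only as a labelled post hoc sensitivity analysis, and claim no Holm or detectable-difference gain from it. For TBES, read (c) as the between-arm result, in line with the belief-change gloss in Research Objectives, with (b) as supportive, and say that this reading was set afterwards. For Knowledge and Self Efficacy the documents give no such lean, so show both estimates and say so. Cost: a few sentences and one extra model per outcome.

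**In both cases** delete 'orthogonal' from the Analytic Plan, because 16 contrasts of rank 9 cannot be orthogonal, and state which time points set (b) covers.
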